Appendix Table 2: List of prohibited medications during study drug treatment

Category	Drug Name
Strong CYP3A4/5 inhibitors	Boceprevir, clarithromycin, cobicistat, conivaptan, elvitegravir, indinavir, itraconazole, ketoconazole, lopinavir, mibefradil, nefazodone, nelfinavir, posaconazole, ritonavir, saquinavir, telaprevir, telithromycin, tipranavir, troleandomycin, voriconazole
Strong CYP3A4/5 inducers	Avasimibe ^{2,3} , carbamazepine, mitotane, phenobarbital, phenytoin, rifabutin, rifampin (rifampicin) ³ , St. John's wort (hypericum perforatum) ³
CYP3A4/5 substrates with NTI ¹	Alfentanil, astemizole, cisapride, cyclosporine, diergotamine (dihydroergotamine), ergotamine, fentanyl, pimozone, quinidine, sirolimus, tacrolimus, terfenadine
Medications with a known risk for QT prolongation ⁴	Amiodarone, arsenic trioxide, astemizole, azithromycin, bepridil, chloroquine, chlorpromazine, cisapride, citalopram, clarithromycin, disopyramide, dofetilide, domperidone, droperidol, erythromycin, flecainide, halofantrine, haloperidol, ibutilide, levomethadyl, mesoridazine, methadone, moxifloxacin, pentamidine, pimozone, probucol, procainamide, quinidine, sotalol, sparfloxacin, terfenadine, thioridazine, vavdetanib
Herbal preparations/medications	Herbal preparations/medications are prohibited throughout the study. These herbal medications include, but are not limited to: St. John's wort, Kava, ephedra (ma huang), ginkgo biloba, dehydroepiandrosterone (DHEA), yohimbe, saw palmetto, and ginseng. Patients should stop using these herbal medications 7 days prior to first dose of study drug.
Other investigational and antineoplastic therapies	Other investigational therapies must not be used while the patient is on the study. Anticancer therapy (chemotherapy, biologic or radiation therapy, and surgery) other than the study treatments must not be given to patients while the patient is on the study medication. If such agents are required for a patient then the patient must be discontinued study drug.

¹ NTI = narrow therapeutic index drugs whose exposure-response indicates that increases in their exposure levels by the concomitant use of potent inhibitors may lead to serious safety concerns (e.g., Torsades de Pointes).
 
² Herbal product
 
³ P-gp inducer
 
⁴ Source: www.crediblemeds.org
	

Appendix A: ECOG Performance Status

Grade	ECOG
0	Fully active, able to carry on all pre-disease performance without restriction
1	Restricted in physically strenuous activity but ambulatory and able to carry out work of a light or sedentary nature, i.e., light house work, office work
2	Ambulatory and capable of all self-care but unable to carry out any work activities. Up and about more than 50% of waking hours.
3	Capable of only limited self-care, confined to bed or chair more than 50% of waking hours.
4	Completely disabled. Cannot carry on any self-care. Totally confined to bed or chair.
5	Dead

Appendix B: Child-Pugh Score

Measure	1 point	2 points	3 points
Total bilirubin (mg/dl)	<2.0	2.0-3.0	>3.0
Serum albumin (g/l)	>3.5	2.8-3.5	<3.5
INR	<1.7	1.7-2.2	>2.2
Ascites	None	Mild (based on clinical findings)	Severe (based on clinical findings)
Hepatic Encephalopathy	None	Controlled Medically	Refractory

5-6 points Child-Pugh A

7-9 points Child-Pugh B

10-15 points Child-Pugh C

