5.0 SUBJECT ELIGIBILITY

Eligibility waivers are not permitted. Subjects must meet all of the inclusion and exclusion criteria to be registered and enrolled to the study. Study treatment may not begin until a subject is registered (See Section 14.3).

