5.1 INCLUSION CRITERIA

- 5.1.1 Histologically confirmed diagnosis of hepatocellular carcinoma (mixed HCC/cholangiocarcinoma is allowed).
- 5.1.2 **RB positivity as defined by RB expression (score of 0.5 or 1) with concurrent p16in4a loss (score of 0-2);**
- 5.1.3 Patients must have HCC limited to the liver. There must be no definitive

clinical or radiographic evidence of extrahepatic HCC. Portal lymphadenopathy is permitted as lymphadenopathy is commonly associated with cirrhosis unrelated to malignancy;

- 5.1.4 Absence of occlusive main portal vein thrombus, branch venous thrombus is allowed;
- 5.1.5 Patients with locally advanced HCC not eligible for curative therapies;
- 5.1.6 Age \geq 18 years;
- 5.1.7 Child-Pugh Score A or B7;
- 5.1.8 ECOG Performance score of 0-2;
- 5.1.9 Anticipated life expectancy greater than 6 months;
- 5.1.10 Following baseline laboratory values should be met:
 - 5.1.10.1** Total bilirubin \leq 2.0 x ULN or direct bilirubin \leq 1.5 x ULN in patients with well-documented Gilbert's Syndrome;
 - 5.1.10.2** INR \leq 1.7;
 - 5.1.10.3** Hgb \geq 9.0 g/dl;
 - 5.1.10.4** Alkaline Phosphatase, AST, ALT $<$ 5 times ULN;
 - 5.1.10.5** Platelet count \geq 75,000/mm³;
 - 5.1.10.6** Serum creatinine \leq 1.5 mg/dL or creatinine clearance \geq 50 mL/min;
 - 5.1.10.7** Absolute neutrophil \geq 1,500 cells/mm³;
 - 5.1.10.8** Potassium, total calcium (corrected for serum albumin), magnesium, and phosphorus within normal limits for the institution or corrected to within normal limits with supplements;
- 5.1.11 Women of childbearing potential must have a negative pregnancy test;
- 5.1.12 Prior therapy is allowed provided the following are met: at least 4 weeks since prior locoregional therapy including surgical resection, radiotherapy, or

ablation. Provided target lesion has increased in size by 25% or more or the target lesion was not treated with locoregional therapy;

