10.3 LABORATORY ASSESSMENTS

Hematology, chemistry, coagulation, urinalysis, and cholesterol panels are to be performed according to the visit schedule outlined in Table 7.1 and 10.1.

Table: 10.1: Clinical Laboratory Parameters Collection Plan

Test Category	Test Name
Hematology	Hemoglobin, Platelets, white blood cells with differential (neutrophils, lymphocytes, basophils, eosinophils, monocytes)
Chemistry	Albumin, alkaline phosphatase, ALT, AST, creatinine, potassium, sodium, glucose, direct bilirubin,

	total bilirubin, total protein, magnesium, phosphorus
Cholesterol and Lipid Panel	Total cholesterol, LDL, HDL, triglycerides
Coagulation	PT, INR
Urinalysis	Glucose, protein, bilirubin, red blood cells, white blood cells, crystals, and bacteria.

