17.3 AMENDMENTS TO THE PROTOCOL

Should amendments to the protocol be required, the amendments will be originated and documented by the Principal Investigator. A summary of changes document outlining proposed changes as well as rationale for changes, when appropriate, is highly recommended. When an amendment to the protocol substantially alters the study design or the potential risk to the patient, a revised consent form might be required.

The written amendment, and if required the amended consent form, must be sent to the IRB for approval prior to implementation.

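### Appendix B's albumin bands overlap and its unit does not fit, so as printed the same patient can score Child-Pugh 7 (eligible) or 8 (excluded)

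*Combined protocol and SAP*

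**What the plan says.** Section 5.1 (criterion 5.1.7) and the study summary limit entry to "Child-Pugh Score A or B7". Section 5.0 adds: "Eligibility waivers are not permitted". Appendix B defines class A as 5 to 6 points and class B as 7 to 9, so a total of 7 is eligible and a total of 8 is not.

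Appendix B is the only Child-Pugh table in the documents. Its albumin row reads "Serum albumin (g/l) >3.5 2.8-3.5 <3.5", the three entries earning 1, 2 and 3 points. Its INR row, by comparison, reads "INR <1.7 1.7-2.2 >2.2".

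Nothing elsewhere settles the albumin score. The baseline laboratory limits in 5.1.10 include no albumin limit. Table 10.1 in section 10.3 names albumin among the chemistry tests ("Albumin, alkaline phosphatase, ALT, AST, creatinine, potassium, sodium, glucose") but gives no unit.

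**The concern.** A scoring table has to give one score for each value. In this row the 2-point and 3-point cells share every value from 2.8 to just under 3.5. The entry rule turns on a single point, so the overlap can decide whether a patient enters. With no waivers there is no provision for settling a borderline case by discretion.

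The unit is a second fault in the same row. If albumin runs in the tens of g/l, a laboratory value applied literally to the printed label lies above 3.5 and scores 1 point however low it is on that scale.

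At stake is consistent application of an eligibility criterion: two staff members scoring the same patient from the same page could reach opposite decisions.

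**Working it through.** There is no planned figure to reproduce. The check is to score values literally from the printed row and follow the total to the entry rule.

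**Inputs.** Albumin bands, the other four items and the class ranges come from Appendix B; the entry rule comes from 5.1.7. Eligible means a total of 7 or less.

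**Step 1: score the albumin row as printed, numbers read in g/dl.**

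| Albumin | Bands met (points) |
|---|---|
| 2.7 | 3 |
| 2.8 | 2 and 3 |
| 3.0 | 2 and 3 |
| 3.4 | 2 and 3 |
| 3.5 | 2 |
| 3.6 | 1 |

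The bilirubin row (below 2.0, 2.0 to 3.0, above 3.0) and the INR row have no such overlap. In both, the 3-point cell begins where the 2-point band ends.

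**Step 2: worked case.** Bilirubin below 2.0 mg/dl (1 point), albumin 3.0 (2 or 3), INR below 1.7 (1), mild ascites (2), no encephalopathy (1).

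- Albumin at 2 points: 1 + 2 + 1 + 2 + 1 = 7, eligible.
- Albumin at 3 points: 1 + 3 + 1 + 2 + 1 = 8, excluded.

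**Step 3: when the overlap changes the decision.** Total = sum of the other four items + albumin points.

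| Other four items | Total, albumin = 2 | Total, albumin = 3 | Decision |
|---|---|---|---|
| 4 | 6 | 7 | eligible either way (class A or B7) |
| 5 | 7 | 8 | eligible or excluded |
| 6 | 8 | 9 | excluded either way |

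Above 6 the patient is also excluded either way. The decision flips only at a sum of 5, that is, with exactly one other item at 2 points and the remaining three at 1.

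**Step 4: the unit.** Albumin of 3.0 g/dl is 30 g/l. Applied literally to the g/l label, 30 exceeds 3.5 and scores 1 point. With other items totalling 6, that gives 6 + 1 = 7 (eligible), whereas reading the numbers in g/dl gives 8 or 9 (excluded). The label, taken literally, can therefore move a decision towards enrolment.

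**The case against.** The strongest reply is that this is a one-cell misprint which the row itself largely exposes. If the 3-point band really covered everything below 3.5, the 2-point band would apply alone only at exactly 3.5, and its printed lower bound of 2.8 would do no work. The neighbouring rows show the pattern that the table follows. Moreover, the overlap bites only once a reader has silently corrected the unit, and someone who does that may well notice the wrong bound too. Finally, 5.1.7 does not cite Appendix B and no section sends staff to it, whereas section 10.2 does cite Appendix A for ECOG status. Staff may score from another version of Child-Pugh.

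Much of this stands. The 2.8 bound does suggest a slip in one cell, and the documents do not show that Appendix B is the table in use. What does not follow is that the row can be left alone. It is the protocol's only scoring table for a criterion without waivers, and as printed it does not return one score.

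A reader might infer that the overlap can only exclude patients wrongly and never enrol them wrongly. The documents do not support that. It holds only if 2 points is the right score in the overlap; if the 3-point cut-off was intended, scoring 2 points would enrol wrongly. Since the cut-offs need clinical confirmation, the direction is open.

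**Conclusion.** The albumin row is wrong as written: an internal inconsistency in a table that bears on eligibility. Its bands overlap from 2.8 to just under 3.5, and its unit does not fit its numbers. The size is one Child-Pugh point, which decides entry when the other four items total 5.

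This rests on two assumptions: that serum albumin is in the tens of g/l, so that the numbers are read in g/dl, and that staff score from Appendix B. The documents give no albumin reference range and do not confirm the second point.

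A reader might go further and infer that patients have been misclassified, or that a given share of the cohort is affected. Counting item combinations cannot show this, because combinations are not weighted by how often they occur. The documents give no basis for a patient count, and no effect on dose-finding or on the PFS analysis is shown. The correction is worth making because it is specific and cheap, not because harm has been demonstrated.

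**What to change.** The sponsor should reconcile the albumin row so that its bands are mutually exclusive and leave no gap, and so that its unit matches its numbers. The clinical team should confirm the cut-offs; this review proposes none. Criterion 5.1.7 should then cite the corrected Appendix B, so that the scoring source is explicit.

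The sponsor should also establish whether Appendix B was used for scoring. If it was, re-check the Child-Pugh eligibility of screened patients whose score depended on the albumin row, both those excluded and those enrolled, because the error can run either way. If it was not, no record check is needed on this ground.

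The cost is a minor amendment, which under section 17.3 "must be sent to the IRB for approval prior to implementation", and, where applicable, a short record check.

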Appendix C: NYHA Classification

Class	Patient Symptoms
I	No limitation of physical activity. Ordinary physical activity does not cause undue fatigue, palpitation, or dyspnea (shortness of breath).
II	Slight limitation of physical activity. Comfortable at rest, but ordinary physical activity results in fatigue, palpitation, or dyspnea.
III	Marked limitation of physical activity. Comfortable at rest, but less than ordinary activity causes fatigue, palpitation, or dyspnea.
IV	Unable to carry out any physical activity without discomfort. Symptoms of cardiac insufficiency at rest. If any physical activity is undertaken, discomfort is increased
